11.5 RETENTION AND REVIEW OF RECORDS

Records and documents pertaining to the conduct of this study, including eCRFs, source documents, consent forms, regulatory documents, clinical laboratory results, calibration logs, or reports (including, but not limited to, all local and central laboratory results and ECG reports), and medication inventory records in all formats (including, but not limited to, written, electronic, magnetic, and optical records, and scans, x-rays, and ECGs) must be retained by the investigator for a period of at least 15 years after study completion unless local regulations or institutional policies require a longer retention period or otherwise notified in writing by the sponsor.

No study records shall be destroyed without notifying the sponsor and providing the sponsor the opportunity to arrange long-term storage for such study records or authorizing in writing the destruction of records after the required retention period.

The investigator must permit access to any documentation relating to the study upon request of the sponsor or applicable regulatory authorities. If the investigator for the study retires, relocates, or for other reasons withdraws from the responsibility of keeping the study records, custody must be transferred to a suitable alternate custodian employee of the institution or to a suitably qualified and responsible third party. The sponsor must be notified in writing of the name and address of the new custodian in advance of the transfer.

2.0 INTRODUCTION

This statistical analysis plan (SAP) provides a more technical and detailed elaboration of the statistical analyses of the efficacy and safety data as outlined and/or specified in the final protocol amendment 2 of RAP-MD-20 (version dated 20 MAY 2019). Specifications of tables, figures, and data listings are contained in a separate document.

RAP-MD-20 is a multicenter, randomized, double-blind, placebo-controlled, parallel-group, 4-week, fixed-dose study comparing rapastinel with placebo in patients with MDD experiencing suicidality. The study will be approximately 5 to 6 weeks in duration and will include the following periods:

- Approximately 5-day screening period
- 4-week double-blind treatment period (DBTP)
- 1-week safety follow-up period

[figure not shown]
Approximately 300 patients are planned to be randomized in the DBTP (150 patients per treatment group).

[figure not shown]
A schematic of the study design is presented in [Figure 3–1](#). The Schedule of Evaluations is provided in Section [3.0](#).

[figure not shown]
Patients will be randomized in a ratio of 1:1 to 1 of 2 treatment groups in DBTP: rapastinel 450 mg IV weekly injection or placebo IV weekly injection. During participation in the study, patients may be treated per local SOC with limited restrictions and IP will be administered in addition to SOC treatments.

Patients completing the DBTP and patients who prematurely discontinue from the study before completing 4 weeks of double-blind treatment should enter the 1-week safety follow-up period.

Additional follow-up visits may be scheduled within 30 days of last dose of IP or last study visit, if necessary for safety reasons.

4.0 STUDY OBJECTIVES

[figure not shown]
The objectives of this study are to evaluate the efficacy, safety and tolerability of rapastinel as a rapid treatment of symptoms of depression and suicidality in adult patients with MDD who are at imminent risk of suicide.

Primary Efficacy Objectives

- To evaluate the efficacy of rapastinel (450 mg IV) versus placebo as a rapid treatment of MDD symptoms in adult patients with MDD who are at imminent risk of suicide, as measured by the change from baseline Montgomery-Asberg Depression Rating Scale (MADRS) total score at 1 day after first dose of investigational product (IP)
- To evaluate the efficacy of rapastinel (450 mg IV) versus placebo as a rapid treatment of suicidality symptoms in adult patients with MDD who are at imminent risk of suicide, as measured by the change from baseline on the Sheehan-Suicidality Tracking Scale (S-STS) total score at 1 day after first dose of IP

Key Secondary Efficacy Objectives:

- To evaluate the efficacy of rapastinel (450 mg IV) versus placebo in the treatment of MDD symptoms, as measured by change from baseline MADRS at 28 Days after first dose of IP.
- To evaluate the efficacy of rapastinel (450 mg IV) versus placebo in the treatment of suicidality symptoms, as measured by the change from baseline on the S-STS total score at 28 Days after first dose of IP.

[REDACTED]

[REDACTED]

[REDACTED]

[REDACTED]

[REDACTED]

[REDACTED]

[REDACTED]

[REDACTED]

[REDACTED]

[REDACTED]

[REDACTED]

[REDACTED]

[REDACTED]

[REDACTED]

[REDACTED]

[REDACTED]

[REDACTED]

[REDACTED]

5.0 ANALYSIS POPULATIONS

The following populations will be considered in the statistical analysis of the study.

5.1 Randomized Population

The Randomized Population will consist of all screened patients who are randomized to a treatment group in the study.

5.2 Safety Population

The Safety Population will consist of all patients in the Randomized Population who took at least 1 dose of randomized IP.

5.3 Modified Intent-to-Treat Population

The modified Intent-to-Treat (mITT) Population will consist of all patients in the Safety Population who had at least 1 postbaseline assessment of the MADRS total score or S-STS total score.

6.0 PATIENT DISPOSITION

The number of patients in the Randomized, Safety, and mITT populations will be summarized by treatment group and study center.

Screen failures (ie, patients screened but not randomized) and the associated reasons for failure to randomize will be tabulated overall for all screened patients.

The number and percentage of patients who complete the DBTP, patients who prematurely discontinue during the same period and who enter the safety follow-up period will be presented for each treatment group and pooled across treatment groups for the randomized population. The reasons for premature discontinuation from the DBTP as recorded on the disposition pages of the eCRFs will be summarized (number and percentage) by treatment group for the randomized population.

6.1 Protocol Deviations

Protocol deviations will be defined in Protocol Deviation Requirement Specification, including significance classification. The number and percentage of patients with significant protocol deviations will be summarized by treatment group for the Randomized Population. A listing of all significant protocol deviations will be provided.

7.0 DEMOGRAPHICS AND OTHER BASELINE CHARACTERISTICS

Demographic parameters (eg, age, race, ethnicity, sex, weight, height, body mass index) and other baseline characteristics will be summarized overall and by treatment group for the mITT Population.

Medical and surgical history, psychiatric history, previous treatment with psychotropic medication, and nondrug psychiatric treatment will be summarized by treatment group for the Safety Population.

Prior medication is defined as any medication taken before the date of the first dose of randomized IP. Concomitant medication is defined as any medication taken on or after the date of the first dose of randomized IP.

Both prior and concomitant medication use will be summarized by the number and proportion of patients in each treatment group receiving each medication within each therapeutic class for the Safety Population. Multiple medication use of the same therapeutic class by a patient will only be counted once.

The *World Health Organization (WHO) Drug Dictionary Enhanced* will be used to classify prior and concomitant medications by therapeutic class and drug name.

8.0 EXTENT OF EXPOSURE AND TREATMENT COMPLIANCE

8.1 Extent of Exposure

The number and percentage of patients who received 1, 2, 3, and 4 randomized IV doses will be summarized by treatment group for the Safety Population. IV administration notes including site reaction at placement of IV, reaction to adhesive, infusion interruption, failure of administration device, increase in suicidality based on clinical evaluation, and perceptual disturbance based on mental status assessment are collected. For each item, the number and percentage of patients who had a 'yes' response will be summarized by treatment group and visit for the Safety Population.

Exposure to the IP for the Safety Population during the DBTP will be summarized for treatment duration, calculated as the number of days from the date of the first dose of double-blind IP taken to the date of the last dose taken during the DBTP, inclusive. Descriptive statistics will be presented by treatment group.

8.2 Measurement of Treatment Compliance

Dosing compliance is defined as the total number of IV doses actually taken by a patient during the DBTP divided by the number of IV doses that were expected to be taken during the DBTP multiplied by 100. Descriptive statistics for IP compliance will be presented by treatment group for each week for the Safety Population.

8.3 Weight-Adjusted Dose of Rapastinel

The dose of rapastinel will be divided by patient baseline weight and summarized descriptively by treatment group for the Safety Population.

9.0 EFFICACY ANALYSES

All efficacy analyses will be based on the mITT Population, unless stated otherwise. The baseline for each specific efficacy endpoint is defined as the last non-missing measurement prior to the first dose of randomized treatment during DBTP.

For efficacy analyses in which study center is a factor, a small center will be defined as a center with < 2 patients in ≥ 1 treatment group in the mITT Population. Small centers will be pooled to form pseudo-centers so that each treatment group includes ≥ 2 mITT patients within the center. Pooling will be done using the following algorithm:

Based on the number of mITT patients, small centers will be ordered from the largest to the smallest, and centers of the same size will be ordered from the largest center code to the smallest center code. The pooling process starts with the largest small center from the top, which will be pooled with the smallest from the bottom until a non-small center is formed. The process will be repeated using the small centers left out after the first pass. If any centers are left out at the end of the process, they will be pooled with the smallest pseudo-center. If there is > 1 smallest pseudo-center, the pseudo-center with the smallest center code will be selected. In case the pseudo-center formed by pooling all small centers is still a small center, it will be pooled with the smallest non-small center. If there is > 1 smallest non-small center, the one with the smallest center code will be selected. These pseudo-centers will be used for all efficacy analyses when the model is adjusted for study center. The efficacy analyses using the mITT Population will be performed based on the treatment to which the patient is randomized regardless of the actual treatment received.

The efficacy analyses of MADRS assessments will be based on the rater-administered MADRS. The MADRS total score is the sum of the 10 individual items. If more than 2 items are missing, then the total score will be set to missing. If there are multiple assessments of MADRS total score for the same nominal visit of a participant, only the last assessment will be used in the analysis.

The efficacy analyses using the mITT population will be performed based on the treatment to which the patient is randomized regardless of the actual treatment received.

9.1 Primary Efficacy Analysis

The primary efficacy parameters will be the change from baseline in MADRS total score and the change from baseline in S-STS total score at 1 day after first dose of treatment. The primary analysis for both primary efficacy parameters will be performed using analysis of covariance (ANCOVA) models with terms for treatment, study center, and baseline. The analysis will be performed based on postbaseline scores using only the observed cases without imputation of missing values. The treatment difference for rapastinel versus placebo will be estimated and reported along with the corresponding 95% CI and the p-value for superiority testing.

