9.7.5 Efficacy Analyses

All efficacy analyses will be based on the ITT Population, unless stated otherwise. The baseline for each specific efficacy endpoint is defined as the last measurement prior to the first dose of randomized treatment. All statistical hypothesis tests will be performed at the 2-sided 5% significance level for main effects. All confidence intervals (CIs) will be 2-sided 95% CIs, unless stated otherwise.

For efficacy analyses in which study center is a factor, a small center will be defined as a center with < 2 patients in ≥ 1 treatment group in the ITT Population. Small centers will be pooled to form pseudo-centers so that each treatment group includes ≥ 2 ITT patients within the center. Pooling will be done using the following algorithm:

Based on the number of ITT patients, small centers will be ordered from the largest to the smallest, and centers of the same size will be ordered from the largest center code to the smallest center code. The pooling process starts with the largest small center from the top, which will be pooled with the smallest from the bottom until a non-small center is formed. The process will be repeated using the small centers left out after the first pass. If any centers are left out at the end of the process, they will be pooled with the smallest pseudo-center. If there is > 1 smallest pseudo-center, the pseudo-center with the smallest center code will be selected. In case the pseudo-center formed by pooling all small centers is still a small center, it will be pooled with the smallest non-small center. If there is > 1 smallest non-small center, the one with the smallest center code will be selected.

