9.2 Secondary Efficacy Analysis

The two key secondary efficacy parameters are:

[figure not shown]
- Change from baseline in MADRS total score at 28 days after first dose of treatment
- Change from baseline in S-STS total score at 28 days after first dose of treatment

Analysis of change from baseline in MADRS total scores and change from baseline in S-STS total score will be performed using mixed-effects model for repeated measures (MMRM) with terms for treatment, study center, visit, baseline, and treatment-by-visit and baseline-by-visit interactions. An unstructured covariance matrix will be used to model the covariance of within-patient scores. The Kenward-Roger approximation will be used to estimate denominator degrees of freedom (Kenward et al, 1997). The treatment difference for rapastinel versus placebo at selected timepoints will be estimated and reported along with the corresponding 95% CI and the p-value for superiority testing.

In the case that the MMRM with unstructured covariance fails to converge with the default algorithm, then the Fisher scoring algorithm will be used to provide better initial values of the covariance parameters; if the model still does not converge, a simplified model without term for study center will be used to find the initial values of the covariance parameters. In the rare event that model still does not converge after using those initial values, simplified covariance structures will be used to fit the model in the following order: (1) ante-dependence, (2) heterogeneous autoregressive, (3) Toeplitz, and (4) compound symmetry. If MMRM still fails to converge, by visit ANCOVA model similar to the primary efficacy analysis will be used for the analysis.

Let H1 and H2 represent the treatment effect comparisons of rapastinel with placebo in regards to the primary efficacy parameters of change from baseline in MADRS total score and change from baseline in S-STS total score at 1 day after first dose of treatment, respectively; and let H3 and H4 represent the treatment effect comparisons of rapastinel with placebo in regards to the secondary efficacy parameters of change from baseline in MADRS total score and change from baseline in S-STS total score at 28 days after first dose of treatment. The graphical procedure displayed in [Figure 9.2-1](#) will be employed to control the overall familywise error rate at $\alpha=0.049$.

Figure 9.2-1. Graphical Testing Procedure

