Specifically, H1 and H2 will be tested at $\alpha=0.0245$ separately. If H1 is rejected, H3 will then be tested at $\alpha=0.0245$. If H2 is rejected, H4 will then be tested at $\alpha=0.0245$. If H3 is rejected but H2 is not rejected, H2 will be further tested at $\alpha=0.049$. If H2 is rejected at $\alpha=0.049$, H4 will be further tested at $\alpha=0.049$. Similarly, if H4 is rejected but H1 is not rejected, H1 will be further tested at $\alpha=0.049$. If H1 is rejected at $\alpha=0.049$, H3 will be further tested at $\alpha=0.049$.

[REDACTED]

[REDACTED]

[REDACTED]

[figure not shown]
[REDACTED]

[REDACTED]

[REDACTED]

[REDACTED]

[REDACTED]

[REDACTED]

[REDACTED]

[REDACTED]

[REDACTED]

[REDACTED]

[REDACTED]

[REDACTED]

[REDACTED]

[REDACTED]

[REDACTED]

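### Do the 95% confidence intervals need to change because the primary tests run at 0.0245 or 0.049?

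*SAP*

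**What the plan says.** SAP 9.1 analyses change from baseline in MADRS and in S-STS at 1 day by ANCOVA. For each, the difference between rapastinel and placebo "will be estimated and reported along with the corresponding 95% CI and the p-value for superiority testing". SAP 9.2 uses nearly the same sentence for the Day-28 key secondary endpoints, where the difference "at selected timepoints will be estimated and reported along with the corresponding 95% CI and the p-value for superiority testing".

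The test levels come from the graphical procedure in SAP 9.2, which has a familywise level of 0.049. It starts from this rule: "H1 and H2 will be tested at $\alpha=0.0245$ separately". H1 is MADRS and H2 is S-STS at Day 1; H3 and H4 are the same scales at Day 28. Rejecting H1 opens H3, and rejecting H2 opens H4. A primary hypothesis that fails at 0.0245 is retested at 0.049 only if the other primary and that primary's Day-28 endpoint are both rejected. SAP 10.6 explains the 0.049: 0.001 is assigned to the interim analysis.

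The protocol sets the default in section 9.7.5: "All confidence intervals (CIs) will be 2-sided 95% CIs, unless stated otherwise". There the tests are at 5%, with a Hochberg procedure for the primary and key secondary endpoints (section 9.7.5.2).

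**The concern.** The SAP lowered the test levels but kept the 95% intervals. A 95% interval excludes zero exactly when the two-sided p-value is below 0.05, and no confirmatory hypothesis in the SAP is tested at that level. The intervals that mirror the tests are 97.55% for a test at 0.0245 and 95.1% for a test at 0.049.

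The main results table could therefore show a primary endpoint with p = 0.038, an interval clear of zero, and a formal result of not rejected. A reader who judges success by the interval would credit an effect that the multiplicity procedure does not support. Protocol section 7.0 says the study is intended to support an application for approval, so this deserves a check. No visible SAP text says that the intervals are unadjusted or descriptive.

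**Working it through.** **Inputs (SAP 11.0 and 9.2).** 150 patients per arm. MADRS: difference 3.76, SD 10. S-STS: difference 4, SD 11. Test levels 0.0245 and 0.049, two-sided. The normal approximation is used throughout, and differences are given as absolute sizes.

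**The plan's own power.** SE = SD × √(2/150), which is 1.155 for MADRS and 1.270 for S-STS. Power ≈ Φ(difference/SE − z). At 0.049, z = 1.969:
- MADRS: Φ(3.256 − 1.969) = 90.1%; the SAP states about 90%.
- S-STS: Φ(3.149 − 1.969) = 88.1%; the SAP states approximately 88%.

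Both reproduce.

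**Interval half-widths, z × SE.**

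| Interval | z | MADRS | S-STS |
|---|---|---|---|
| 95% | 1.960 | 2.26 | 2.49 |
| 95.1% | 1.969 | 2.27 | 2.50 |
| 97.55% | 2.249 | 2.60 | 2.86 |

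The 95% interval is 13% shorter than the 97.55% one (1 − 1.960/2.249). Against the 95.1% interval the difference is about 0.01 point.

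**Example.** An observed MADRS difference of 2.40 gives p = 0.038. The 95% interval is 0.14 to 4.66 and the 97.55% interval is −0.20 to 5.00.

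**Chance that p falls between 0.0245 and 0.05.** This is power at 0.05 minus power at 0.0245:
- MADRS at 3.76: 0.9026 − 0.8430 = 0.060.
- S-STS at 4: 0.8828 − 0.8159 = 0.067.
- No effect: 0.05 − 0.0245 = 0.0255 per endpoint.

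For the band from 0.049 to 0.05 the chances are 0.0015 (MADRS), 0.0017 (S-STS) and 0.001 (no effect).

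**Chance of a contradiction in the final result.** An endpoint with p between 0.0245 and 0.049 still passes if the other primary and that primary's Day-28 endpoint are rejected. Let q be the power of that Day-28 test at 0.0245. The documents give no Day-28 effect, so q is an assumption. With independent endpoints,

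P(contradiction) = band − (power of the other primary at 0.0245) × q × (band − narrow band).

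- MADRS: 0.0595 − 0.8159 × q × 0.0580.
- S-STS: 0.0669 − 0.8430 × q × 0.0652.

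| Assumed q | MADRS | S-STS |
|---|---|---|
| 0 (never passed on) | 6.0% | 6.7% |
| 0.0245 (no Day-28 effect) | 5.8% | 6.6% |
| 0.80 | 2.2% | 2.3% |
| 1 | 1.2% | 1.2% |

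If the two primaries are correlated at 0.5 and q is 0.80, simulation gives about 3% for each.

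**Does any decision use the interval?** SAP 9.1 asks for an estimate, an interval and a p-value. SAP 9.2 defines rejection only by comparing p-values with the graph's levels. Neither section makes exclusion of zero a criterion.

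**The case for a change.** The strongest case for a change is that the mismatch is real, arises in two primary endpoints, and would cost one sentence to remove. The SAP's word for the interval can be read as tying it to the superiority test, and a 95% interval does not match a test at 0.0245. Under any assumption about Day 28 the chance of a contradiction stays above zero, and the question is better settled before unblinding than argued over afterwards.

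The arithmetic stands, and so does the point that a label would help. The rest is weaker. The sentence reads at least as naturally with the interval belonging to the estimated difference, and a 95% interval for that difference has its stated coverage whatever alpha is allotted to the test.

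Matching the interval to the test level is also not a clean remedy. H3 and H4 have no level when the hypothesis before them is not rejected, because they are then never tested. A primary that is retested has been examined at two levels. Choosing 97.55% or 95.1% after seeing the other endpoints makes the level depend on the data, and nobody has shown that such intervals keep their nominal or joint coverage. Fixed 95% intervals beside a separate multiplicity procedure are a defensible convention.

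Parts of SAP section 9 are redacted and the table specifications are in a separate document, so a clarifying note may already exist.

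**Conclusion.** The observation is correct, but it does not call for a change. Following the SAP as written gives the right decisions: the graphical procedure alone determines success, the error rate is unaffected, and the reported intervals are valid as 95% intervals for single differences.

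What remains is a possible mismatch of appearance. At the planning effects, with 150 observed patients per arm, its probability is at most about 6.0% (MADRS) and 6.7% (S-STS). With independent endpoints it falls to about 1.2% each as the assumed Day-28 power rises to 100%. Where a primary is retested at 0.049 the mismatch is negligible. The half-widths rest on the planning SDs and ignore covariate adjustment and missing Day-1 data. The p-value limits of the mismatch, 0.0245 to 0.05, do not depend on those assumptions.

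The missing label is the sort of detail that analysts normally supply in a table footnote. Adding it would be harmless, and leaving it out alters no estimate, test or conclusion.
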